#### CONFIDENTIAL

This material is the property of the NYU School of Medicine and Langone Medical Center. Do not disclose or use except as authorized in writing by the study sponsor

Given that this research study is of short duration (60 days) there is no reasonable expectation that there to be a change in capacity during the time period of the study and will therefore not monitor for capacity beyond the initial visit.

### **5.5 Duration of Study Participation**

This study will last at most 65 days from recruitment to completion. The total duration is intended to be 60 days, however, for the interim study visits (visits 2 and 3) we will allow the visit +/- 3 days to allow for PWD-caregiver schedule, and at visit 4, up to +5 days leeway.

### **5.6 Total Number of Participants and Sites**

Recruitment will end when approximately 345 dyads (345 PWD and 345 caregivers) are enrolled. It is expected that approximately 345 dyads will be enrolled in order to produce 300 evaluable dyads.

Sample at VNAHG Site: 207 dyads (207 PWD, 207 caregivers) enrolled, with expectation of 180 complete dyad cases (180 PWD, 180 caregivers).

Sample at University of Utah Site: 86 dyads enrolled (86 PWD, 86 caregivers) with expectation of 75 complete dyad cases (75 PWD, 75 caregivers).

Sample at University of Miami Site: 52 dyads enrolled (52 PWD, 52 caregivers) with expectation of 45 complete dyad cases (45 PWD, 45 caregivers).

### **5.7 Participant Withdrawal or Termination**

#### **5.7.1 Reasons for Withdrawal or Termination**

The primary potential cause for withdrawal from the study is if either member of the dyad chooses to withdraw from the study at any point.

Participants are free to withdraw from participation in the study at any time upon request. An investigator may terminate participation in the study if:

- The participant meets an exclusion criterion (either newly developed or not previously recognized) that precludes further study participation
- The study team is unable to maintain or appropriately reschedule study appointments.

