#### 5.2 Exclusion Criteria

An individual who meets any of the following criteria will be excluded from participation in this study.

1. Patients with a separate Axis 1 diagnosis other than forms of dementia, depression or anxiety.
2. PWD residing in assisted living facilities or board and care homes
3. PWD solely receiving infusion or home health aide services.

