The legal surrogate will be verified by either the HHC agency or through written documentation. Should they not have written documentation of being an appointed surrogate, the law of the state of residence will determine the priority order for determining the surrogate, which is as follows:

Florida: spouse, adult child, parent, adult sibling, close friend

New Jersey: spouse, adult child, parent, sibling, close friend

Utah: spouse, adult child, parent, sibling, grandchild, grandparent, individual who is healthcare proxy

Because PWD in HHC are primarily homebound, tend to receive HHC for at least 60 days, with follow-up is provided through scheduled home visits, we do not anticipate significant retention problems. Additionally, the study burden is minimal, requiring approximately an hour per dyad at baseline and 60-days, and 20 minutes at the 15 and 30 days. Study staff will obtain detailed contact information for the PWD, caregiver, and where applicable proxy, will schedule the follow-up visits at the initial visit, email or text the visit schedule to the caregiver (based on caregiver preference; no PHI or PII included, see templates), and call 4 days and 1 day prior to each follow-up appointment to confirm and/or reschedule.

The greatest risks to retention are re-hospitalization and institutionalization, either for short-term post-acute rehabilitation after a re-hospitalization or long-term institutionalization for ADRD. Subjects are not required to attend the intermediate and final visits together. Efforts to accommodate the subjects' schedules will be considered in data collection. Phone interviews with the PWD and caregiver to collect participant survey data will occur for all time points. If both subjects are unavailable to complete an intermediate visit, the visit will be recorded as missed. To maintain subject retention, subjects will be terminated from the study only if the caregiver, as respondent, does not complete visit four.

Dyads will be enrolled starting in month 6 of year 1 and continuing through month 9 of year 4 (3 years, 3 months). Follow-up will continue through Month 2 of year 5. The investigators therefore anticipate recruiting 9 new dyads per month at all sites throughout the 4 years, with 5-6 through the VNA Health Group, 2-3 at the University of Utah and 1-2 at University of Miami.

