#### **5.7.2 Handling of Participant Withdrawals or Termination**

Given the minimal risk nature of this study, individuals who chose to withdraw from the study will not continue to be followed in any form. We have factored in a 15% study non-completion rate and anticipate recruiting 345 dyads to meet the 300 dyads required study participants. Subjects will not be disenrolled based on data related issues. If subjects are unable to attend intermediate visits (Visit 2 and/or 3), those visits will be counted as missed. If the caregiver does not complete visit four, both subjects will be terminated from the study.

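### Section 5.7.1 permits termination for an exclusion that arises after enrolment, which does not fit the single ground in 5.4 and can cause avoidable loss of day-60 data

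*Combined protocol and SAP*

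**What the plan says.** After allowing voluntary withdrawal, section 5.7.1 gives a discretionary power: "An investigator may terminate participation in the study if" one of two conditions holds. The first is "The participant meets an exclusion criterion (either newly developed or not previously recognized) that precludes further study participation". The second is that study appointments cannot be kept or rescheduled.

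Section 5.2 lists three exclusions. The first concerns psychiatric diagnosis. The other two are "PWD residing in assisted living facilities or board and care homes" and "PWD solely receiving infusion or home health aide services".

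Section 5.4 states that "subjects will be terminated from the study only if the caregiver, as respondent, does not complete visit four". Section 5.7.2 repeats the rule without the word *only*: "If the caregiver does not complete visit four, both subjects will be terminated from the study". Section 5.3 adds that a PWD who becomes distressed by taking part is withdrawn.

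On what follows removal, 5.7.2 says that "individuals who chose to withdraw from the study will not continue to be followed in any form". It is silent on people whom the investigator terminates. Section 8.8.2 replaces withdrawals with completed cases, and 10.5 recruits until each cluster has 15 completed cases. Section 10.3 names data sets but defines no analysis population. Section 10.4.3 compares those retained with those withdrawn or terminated.

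**The concern.** Exclusion criteria screen people at entry. Used after enrolment, when the care team's arm is already set, they become a rule that removes people for something that happened during follow-up. Where the PWD lives and which services continue can both change within 60 days. The DSM-H aims to change behaviour, symptoms and quality of life, which may influence a move, so the share removed could differ between arms.

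The removal would also be avoidable. Section 3.1 makes the Aim 1 primary outcome caregiver-rated, the Aim 2 primary outcome is the caregiver's own quality of life, and Aim 3 utilization comes from caregiver interview. Section 5.4 provides telephone interviews at all time points. A caregiver who still consents can supply all three after a change of residence or service. Outcomes that are not collected at day 60 cannot be recovered later.

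**Working it through.** **The rules side by side**

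- 5.4: one ground for termination, namely that the caregiver does not complete visit four.
- 5.7.1, first condition: a newly met exclusion. This is a different ground and can apply while the caregiver is still available.
- 5.7.1, second condition: appointments cannot be kept. This is wider than visit four.
- 5.3: withdrawal for distress. Again a different ground.
- 5.7.2: repeats the visit-four rule and does not mention a newly met exclusion.

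Read literally, the exclusive wording in 5.4 cannot stand beside the other three grounds. Nothing says which section prevails.

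**The plan's own figures (10.5)**

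Inputs: 20 clusters, 15 dyads each, ICC .05, alpha .05 (two-sided assumed), detectable effect .45, QOL-AD SD 5.9.

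- Variance of the contrast = 4 × (0.05 + 0.95/15) / 20 = 0.0227, so the standard error is about 0.15 SD.
- With 18 degrees of freedom, power at .45 is 0.807. The stated .80 is reproduced.
- Recruitment: 300 × 1.15 = 345, as stated. The margin is 345 − 300 = 45 dyads, or 45/345 = 13.0%.

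**How many dyads (assumption; the documents give no rate)**

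If 5 to 10% of PWD had such a change and every one were terminated: 345 × 0.05 = 17 and 345 × 0.10 = 35 dyads. Some of these may already be counted in the 15% non-completion allowance, so they should not simply be added to it.

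**Shift in the QOL-AD contrast**

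Suppose removed PWD score k SD below retained PWD. In each arm the retained-only mean then exceeds the full mean by k × π, where π is the share removed. The contrast (DSM-H minus control) shifts by k × (π in DSM-H − π in control). All values of k and π are assumptions.

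| Control removed | DSM-H removed | Shift, k = 0.5 | Shift, k = 1.0 |
|---|---|---|---|
| 10% | 6% | −0.02 SD | −0.04 SD |
| 10% | 5% | −0.025 SD | −0.05 SD |
| 13% | 5% | −0.04 SD | −0.08 SD |
| 5% | 10% | +0.025 SD | +0.05 SD |
| 5% | 5% | 0 | 0 |

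In QOL-AD points, 0.02 × 5.9 = 0.12 and 0.08 × 5.9 = 0.47. Relative to the standard error, 0.02/0.15 = 0.13 and 0.08/0.15 = 0.53.

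**Aim 3 illustration (assumptions)**

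Section 4.2.1 treats a 10% reduction as meaningful. Take 10% of control and 6% of DSM-H dyads removed, equal event rates among those retained, and all utilization of removed dyads lost.

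- Removed dyads at twice the retained rate: the full rates are 0.90 + 0.10 × 2 = 1.10 and 0.94 + 0.06 × 2 = 1.06. The ratio is 1.06/1.10 = 0.96, against 1.00 in the retained.
- At three times the rate: 1.12/1.20 = 0.93, against 1.00.

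The hidden difference is about 4 to 7%, roughly one to two thirds of the 10% target. Reversing the removal rates reverses the direction. Keeping utilization already reported at day 30 would reduce it.

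**The case against.** The strongest reply is that the clause is narrow and the conflict is one of wording. Termination is discretionary, and the exclusion must be one that precludes further participation. If the caregiver can still be telephoned, a move arguably precludes nothing and the clause never applies. The sentence in 5.4 follows the rule on missed intermediate visits and can be read as a missed-visit rule: visits 2 and 3 do not cost enrolment, visit 4 does. It cannot be a complete list, since 5.7.1 allows voluntary withdrawal and 5.3 withdraws distressed PWD. Section 10.4.3 already plans a comparison that includes terminated subjects.

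Much of this stands. A reader might infer that the protocol obliges sites to remove anyone who moves or loses skilled care. It does not. A reader might also infer that the dyads removed are the institutionalised ones with the poorest course, since 5.4 says that "The greatest risks to retention are re-hospitalization and institutionalization". The documents do not support that either. In 5.4 those words cover post-acute rehabilitation and long-term institutionalization for dementia, while 5.2 lists only assisted living and board and care; nursing homes and rehabilitation stays are not named. Aide-only status may reflect improvement or service rules. The two examples come from applying 5.2; section 5.7.1 does not name them.

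What does not stand is that the text is therefore safe. The preclusion qualifier is undefined, so an investigator could reasonably take meeting an exclusion as enough. The contextual reading of 5.4 is possible, but its words are exclusive. The 10.4.3 comparison describes who was lost and does not restore their outcomes. The 15% allowance covers numbers, not selection.

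One limit on the remedy: pain is assessed on the PWD, and the visit lists place QOL-AD among surveys that depend on the QDRS score, although 3.1 and Table 2 make it caregiver-rated. Continued follow-up secures the caregiver-reported outcomes, not every measure.

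**Conclusion.** The inconsistency is real, and the removal that it permits is avoidable. Section 5.7.1 allows, without requiring, termination for a change of residence or service after enrolment. That does not fit 5.4, and no section keeps terminated dyads in follow-up or analysis.

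A reader might go further and conclude that the primary comparison is materially biased. The documents do not support this. They give no rate of such changes and no rule that turns each one into a termination. Under the assumed rates the QOL-AD shift is about 0.02 to 0.08 SD against .45, about half a standard error at most. Its direction cannot be known in advance, and it is zero if both the rates and the deficits are equal across arms. Aim 3 could be more exposed because its target is small, but that illustration also rests wholly on assumed rates.

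The case for acting rests on low cost and on data that cannot be recovered, not on the size of the bias. It is a cheap improvement, not a must-fix.

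**What to change.** - In 5.7.1, delete the words on newly developed exclusions and state that the 5.2 criteria are applied at enrolment. Ineligibility that existed at baseline but was missed is a separate, lesser matter and can keep its own rule.
- Add a sentence on these lines: a change of residence, an end to skilled home health care, or a change to infusion-only or aide-only services after enrolment is recorded with its date and is not a reason for termination; for dyads still consenting, caregiver-reported outcomes and utilization are collected through day 60.
- In 10.3, state that such dyads stay in the analysis. In 8.8.2, state that they are not replaced.
- Reconcile 5.3, 5.4, 5.7.1 and 5.7.2 so that one list gives every ground for withdrawal or termination, including distress and appointments that cannot be kept.

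The cost is protocol wording, with the IRB review that 13.2 requires for any amendment, and a few extra telephone interviews with caregivers who have already consented.

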#### **5.7.2 Handling of Participant Withdrawals or Termination**

Given the minimal risk nature of this study, individuals who chose to withdraw from the study will not continue to be followed in any form. We have factored in a 15% study non-completion rate and anticipate recruiting 345 dyads to meet the 300 dyads required study participants. Subjects will not be disenrolled based on data related issues. If subjects are unable to attend intermediate visits (Visit 2 and/or 3), those visits will be counted as missed. If the caregiver does not complete visit four, both subjects will be terminated from the study.

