### 7.2.7 Withdrawal/Early Termination Visit

Should individuals withdraw from the study for any reason, we will attempt to ask for the reason and ask if any SAE or AE have occurred if the PWD/caregiver are reachable. We will also if withdrawal is for non-communication with the study team we will review the HHC medical record to ascertain if there was an SAE or AE.

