## 8 Assessment of Safety

- 8.1 This study is a minimal risk study given that it is an evidence-based implementation science intervention. However, the investigators will monitor for the following safety parameters and events throughout this study. In instances where an adverse event (AE) or a serious adverse event (SAE) has been identified, the investigators will follow standard clinical practice (SCP) whereby the investigator will notify the subject's health care provider responsible for initiating and/or approving the subject's enrollment into HHC services. In situations where an AE or SAE has been determined to be related to the study and the subject has withdrawn, investigators will actively monitor in follow up. Specification of Safety Parameters

CONFIDENTIAL

This material is the property of the NYU School of Medicine and Langone Medical Center. Do not disclose or use except as authorized in writing by the study sponsor  
 Interventional Template Version: 28 APR 2017

Due to the pragmatic nature of the trial, the DSMB has directed this trial to perform a highly focused AE collection process which requires following single adverse event: a PHQ-9 score worsened by greater than or equal to 5 points during the course of the study. The DSMB further requires monitoring the following severe AEs: Caregiver attempted suicide; death of caregiver; death of person with dementia a; medical event that may jeopardize the subject, including hospitalization of either the person with dementia or caregiver, suicidal ideation, elder neglect or abuse, or an environmental threat such as unsecured firearm.

In cases of the following safety parameters, the site-PI and PI shall be notified immediately, a telephone triage performed, and then SCP will be followed by notifying the subject's primary care provider to advise of the situation.

Due to the virtual nature of data collection, safety monitoring will be done to the best of abilities for:

- Imminent home safety threats/hazards (e.g. hoarding/cluttering, unsecured gun).**
- Suspected elder abuse or neglect.**

**Caregiver Depression:** Should caregivers have a score of  $\geq 10$  on the PHQ-9 or exhibit suicidal ideation via item 9 of the PHQ-9 or verbally outside of any instrumentation, Definition of Adverse Events (AE)

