## 8.3 Time Period and Frequency for Event Assessment and Follow-Up

The occurrence of an AE or SAE may come to the attention of study personnel during study visits and interviews of a study participant presenting for medical care, or upon review by a study monitor. All AEs including local and systemic reactions not meeting the criteria for SAEs will be captured on the appropriate RF. Information to be collected includes event description, time of onset, clinician's assessment of severity, relationship to study product (assessed only by those with the training and authority to make a diagnosis), and time of resolution/stabilization of the event. All AEs occurring while on study must be documented appropriately regardless of relationship. All AEs will be followed to adequate resolution.

Any medical condition that is present at the time that the participant is screened will be considered as baseline and not reported as an AE. However, if the study participant's condition deteriorates at any time during the study, it will be recorded as an AE. UPs will be recorded in the data collection system throughout the study.

Changes in the severity of an AE will be documented to allow an assessment of the duration of the event at each level of severity to be performed. AEs characterized as intermittent require documentation of onset and duration of each episode.

The PI will record all reportable events with start dates occurring any time after informed consent is obtained until 7 (for non-serious AEs) or 30 days (for SAEs) after the last day of study participation. At each study visit, the investigator will inquire about the occurrence of AE/SAEs since the last visit. Events will be followed for outcome information until resolution or stabilization.

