All unresolved adverse events should be followed by the investigator until the events are resolved, the subject is lost to follow-up, or the adverse event is otherwise explained. At the last scheduled visit, the investigator should instruct each subject to report any subsequent event(s) that the subject, or the subject's personal physician, believes might reasonably be related to participation in this study. The investigator should notify the study sponsor of any death or adverse event occurring at any time after a subject has discontinued or terminated study participation that may reasonably be related to this study. The sponsor should also be notified if the investigator should become aware of the development of cancer or of a congenital anomaly in a subsequently conceived offspring of a subject that has participated in this study.

CONFIDENTIAL

This material is the property of the NYU School of Medicine and Langone Medical Center. Do not disclose or use except as authorized in writing by the study sponsor

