## **8.5 Reporting Procedures – Notifying the Study Sponsor**

The study clinician will complete a SAE Form within the following timelines:

- All deaths and immediately life-threatening events, whether related or unrelated, will be recorded on the SAE Form. SAE that have been determined to be related to the study will be submitted to the DSMB/study sponsor within 24 hours of site awareness. See Section 1, Key Roles for contact information.
- Other SAEs that are determined to be related to the study will be submitted to the DSMB/study sponsor within 72 hours of site awareness.

All SAEs will be followed until satisfactory resolution or until the site investigator deems the event to be chronic or the adherence to be stable. Other supporting documentation of the event may be requested by the DSMB/study sponsor and should be provided as soon as possible.

As a follow-up to the initial report, within the following 48 hours of awareness of the event, the investigator shall provide further information, as applicable, on the unanticipated event or the unanticipated problem in the form of a written narrative. This should include a copy of the completed Unanticipated Problem form,

CONFIDENTIAL

This material is the property of the NYU School of Medicine and Langone Medical Center. Do not disclose or use except as authorized in writing by the study sponsor

and any other diagnostic information that will assist the understanding of the event. Significant new information on ongoing unanticipated adverse effects shall be provided promptly to the study sponsor.

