### **8.8.2 Frequency and Reporting**

As noted in [section 8.4](#), all AE and SAE will be reported directly to the site PI and then study PI. All events will be reported within 24 hours to the DSMB and the IRB at both the study site and the primary IRB (NYU). The DSMB will then discuss whether and how to convene. Outside of SAE, the DSMB will meet at least prior to onset of the trial and every 6 months at a minimum. Safety reports will be sent twice yearly including analysis of study progress and data and safety issues. These reports will include descriptive analyses of participant demographic data, interim analyses of primary and secondary outcomes, as well as any adverse or serious adverse events, and quality improvement program fidelity. Individuals who withdraw from the trial will be examined in sensitivity analyses, however will be replaced with completed cases for the purposes of the trial. There are no cases where the quality improvement program will be discontinued but follow-up will still occur unless an individual withdraws from the study due to an AE or SAE, in which case we will ensure safety of the individual/dyad and referral to existing resources.

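### Section 5.7.2 stops all follow-up of subjects who choose to withdraw, which contradicts the safety follow-up in Sections 8.1, 8.3 and 8.5

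*Combined protocol and SAP*

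**What the plan says.** The withdrawal rule is in Section 5.7.2. It cites the study's minimal risk and says that "individuals who chose to withdraw from the study will not continue to be followed in any form". It gives no exception and no cross-reference to Section 8.

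The safety sections say otherwise:

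- **Section 8.1** covers an AE or SAE found to be "related to the study and the subject has withdrawn, investigators will actively monitor in follow up". Its list of serious events to monitor, set by the DSMB, includes a "medical event that may jeopardize the subject, including hospitalization of either the person with dementia or caregiver".
- **Section 8.3**: "All unresolved adverse events should be followed by the investigator until the events are resolved, the subject is lost to follow-up", or the event is otherwise explained.
- **Section 8.5**: "All SAEs will be followed until satisfactory resolution or until the site investigator deems the event to be chronic" or stable.
- **Section 8.8.2** says follow-up does not outlast the program "unless an individual withdraws from the study due to an AE or SAE, in which case we will ensure safety of the individual/dyad" and give a referral.
- **Section 7.2.7** asks about AEs and SAEs once, at withdrawal for any reason, if the dyad can be reached.
- **Section 13.4** applies even when a subject revokes authorization to use health information. Staff should still try to get permission to learn at least vital status at the end of the scheduled period.

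**The concern.** Section 5.7.1 names a dyad member's decision to leave as the primary potential cause of withdrawal, so the rule in 5.7.2 governs the ordinary case. A site that applies it literally would drop safety follow-up that Section 8 requires. A site that applies Section 8 would break 5.7.2. Both texts are in force, and neither says which prevails.

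What is at stake is whether serious events already open at withdrawal are followed to an outcome and handled the same way at all three sites. The DSMB reviews SAEs, and Section 8.7 halts the study if SAEs are found to be caused by the program.

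**Working it through.** No arithmetic applies, because the plan states no figure on this point. The check sets the rules side by side for each kind of subject who chooses to withdraw.

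| Situation at withdrawal | Section 5.7.2 | Other sections | Result |
|---|---|---|---|
| Open event, judged study-related | Stop | 8.1: monitor actively | Literal contradiction; resolved if 8.1 is read as a specific exception |
| Subject leaves because of an AE or SAE | Stop | 8.8.2: ensure safety and refer | Resolved if 8.8.2 is read as an exception |
| Open SAE, judged unrelated; subject leaves for another reason | Stop | 8.5: follow until resolved, chronic or stable | **Contradiction remains** |
| Open non-serious AE, judged unrelated; subject leaves for another reason | Stop | 8.3: follow until resolved, lost or explained | Contradiction on paper; almost no cases (step 3) |
| No event known | Stop | 7.2.7: one enquiry if reachable | Workable |

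1. *Do the two exceptions cover the third row?* No. Section 8.1 needs a finding that the event is related. Section 8.8.2 needs the event to be the reason for leaving. For illustration, suppose the person with dementia is in hospital for a cause judged unrelated, and the caregiver ends participation because the interviews take too long. Neither exception is triggered.

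2. *Does a listed end point cover it?* Section 8.5 lists resolution, chronicity and stability. Section 8.3 adds loss to follow-up and an event otherwise explained. Choosing to withdraw is none of these. Loss to follow-up is not the same thing either: Section 7.2.7 gives withdrawal for non-communication its own handling, apart from withdrawal for other reasons.

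3. *How much of this concerns non-serious AEs?* Very little. Section 8.1 limits AE collection to one event, a PHQ-9 worsening of at least 5 points. Section 3.2, the visit lists in Section 7.2 and Table 2 schedule the PHQ-9 only at days 0 and 60. A caregiver who leaves before visit 4 has one scheduled score, so no scheduled worsening can be computed. The practical gap is therefore mainly SAEs.

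**The case against.** The best defence is that the protocol has a coherent rule: no follow-up by default, with exceptions for related events (8.1) and for withdrawal due to an event (8.8.2). That reading is fair and settles the first two rows of the table. It does not settle the third, and the reader has to supply it, because 5.7.2 says there is no follow-up of any kind.

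A second defence is that some unrelated events already have an exit. Section 8.2.2 lets an event be called unrelated when another cause is established, and 8.3 ends follow-up once an event is otherwise explained. This shrinks the group. It does not empty it, because 8.5 covers all SAEs and lists no such exit.

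Third, Sections 8.4 and 8.6 send every event to the study PI and involve the site PIs in classification. That makes different handling by site less likely, and this point stands.

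A reader might go further and infer that Section 7.2.7 wrongly leaves out people who choose to leave, because its chart check applies only "if withdrawal is for non-communication with the study team we will review the HHC medical record". The documents do not support that. Asking those who can be reached, and checking records for those who have gone silent, is a reasonable design. Section 8.3 does record events "until 7 (for non-serious AEs) or 30 days (for SAEs) after the last day of study participation", but it prescribes no active search of records in that period. Extending the chart check would resolve no contradiction.

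**Conclusion.** Section 5.7.2 is wrong as written, and the fault is minor. Its unqualified ban contradicts 8.1, 8.3 and 8.5. After every reasonable exception is allowed, it still conflicts with the SAE rule for an open, unrelated SAE in a subject who leaves for another reason.

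The size is not known. A reader might take the planned shortfall of 345 − 300 = 45 dyads as the number affected. That figure counts all planned non-completion, including dyads terminated because the caregiver missed visit 4, and says nothing about open SAEs. A reader might also infer from Section 5.4, which names re-hospitalization as a leading retention risk, that the case is common. A dyad that leaves because of a hospital stay falls under 8.8.2 instead. The affected group is probably small.

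No planned efficacy estimate, power or alpha depends on this. The conclusion rests on the protocol text alone. The Study Manual and consent forms were not available. The manual may hold a working rule, but Section 18 says that attachments are not part of the protocol, so it would not remove the contradiction.

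**What to change.** Replace the sentence in 5.7.2 with wording such as: *Individuals who choose to withdraw will have no further outcome interviews. Unless they refuse, follow-up of AEs and SAEs already identified continues under Sections 8.1, 8.3 and 8.5.* Ask for this permission at the withdrawal contact already planned in Section 7.2.7. That keeps it in line with the permission-seeking approach of Section 13.4 and leaves the subject free to decline.

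The cost is one amendment with IRB approval under Section 13.2 and a check against the consent forms. If those forms have to change, the IRB process also requires a decision on re-consent. The amendment adds no assessment or record review, and it requires no follow-up beyond what Section 8 already asks for. If the Study Manual already gives a rule, 5.7.2 should also cite it.
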